TND	target not detected
ULN	upper limit of the normal range
VEL	velpatasvir (GS-5816)
WBC	white blood cell
WHO	World Health Organization

1. INTRODUCTION

This statistical analysis plan (SAP) describes the statistical analysis methods and data presentations to be used in tables, figures, and listings (TFLs) in the clinical study report (CSR) for Study GS-US-342-1518. This SAP is based on the study protocol amendment 1 dated 21 April 2015 and the electronic case report form (eCRF). The SAP will be finalized before database finalization. Any changes made after the finalization of the SAP will be documented in the CSR.

1.1. Study Objectives

The primary objectives of this study are as follows:

- To evaluate the efficacy of treatment with sofosbuvir (SOF)/velpatasvir (VEL, GS-5816) fixed dose combination (FDC) for 12 weeks in subjects with chronic HCV infection as measured by the proportion of subjects with sustained viral response 12 weeks after cessation of treatment (SVR12)
- To evaluate the safety and tolerability of treatment with SOF/VEL for 12 weeks

The secondary objectives of this study are:

- To determine the proportion of subjects with SVR at 4 and 24 weeks after cessation of treatment (SVR4 and SVR24)
- To evaluate the proportion of subjects with virologic failure
- To evaluate the kinetics of circulating HCV RNA during treatment and after cessation of treatment
- To evaluate the emergence of viral resistance to SOF and VEL during treatment and after cessation of treatment

The exploratory objectives of this study are:

P
P
D

I

1.2. Study Design

This is an international, multicenter, open-label study that will evaluate the safety, tolerability and antiviral efficacy of SOF/VEL for 12 weeks in treatment-naïve and treatment-experienced adults with chronic HCV infection. Subjects with or without cirrhosis will be enrolled.

Approximately 20% of subjects may be treatment experienced and approximately 20% of subjects may have compensated cirrhosis at screening.

Subjects with chronic HCV infection will be enrolled to receive SOF/VEL once daily for 12 weeks.

This multi-regional clinical trial (MRCT) is planned to be conducted in China, Malaysia, Singapore, Thailand, and Vietnam. China will be considered Region 1. Malaysia, Singapore, Thailand, and Vietnam, which are all located in Southeast Asia, will be considered Region 2.

Approximately 360 subjects will be enrolled in the study in total. The approximate number of subjects to be enrolled in each region according to HCV genotype is represented in the table below:

HCV GT (Prior Rx History)	GT-1 (TN, TE)	GT-2 (TN, TE)	GT-3 (TN, TE)	GT-4,5,6 (TN, TE)	Total
Region 1 (China)	80	60	60	60	260
Region 2 (Malaysia, Singapore, Thailand, Vietnam)	100				100

Rx = Treatment
 TN = Treatment Naïve, TE = Treatment Experienced

It is expected that a small number of subjects whose HCV genotype cannot be determined by the central laboratory (HCV genotype indeterminate) may also be enrolled.

The schedule of assessments is provided as an appendix to the SAP ([Appendix 1](#)).

The total time to complete all study visits is up to approximately 42 weeks including the following periods:

- 42-day (6-week) screening period
- 12-week treatment period
- Up to 24-week posttreatment period

1.3. Sample Size and Power

The sample size justification is based on the Region 1 population. A sample size of 260 subjects in Region 1 will provide more than 80% power to detect an improvement of at least 6 percentage points in SVR12 rate from the performance goal of 85% by using a two-sided exact one-sample binomial test at the significance level of 0.05.

In addition, a confidence interval approach will be used to estimate the SVR12 rates for Region 2 and for the overall population (ie, combined Region 1 and Region 2). With 100 subjects from Region 2, and 360 subjects from the overall population, the 2-sided 95% exact CIs for different observed SVR12 rates are presented in the table below.

Region	Observed SVR12 rate	2-sided 95% exact CI
Region 2 (n=100)	80% (80 out of 100)	71% - 87%
	90% (90 out of 100)	82% - 95%
Overall (n=360)	80% (288 out of 360)	75% - 84%
	90% (324 out of 360)	86% - 93%

2. TYPE OF PLANNED ANALYSIS

2.1. Data Monitoring Committee

This study does not have a data monitoring committee (DMC).

2.2. Interim Analysis

2.2.1. Posttreatment Week 4 Analysis

A Posttreatment Week 4 analysis will be conducted for administrative purposes after all subjects complete the Posttreatment Week 4 visit or prematurely discontinue from the study. All safety and efficacy data through the Posttreatment Week 4 visit will be included (SVR12 will not be evaluated at this time). The results will be restricted to a limited group of individuals within Gilead Sciences, Inc. (Gilead). There will be no changes to the study design, study conduct, or the sample size as a result of this administrative analysis.

2.2.2. Primary Efficacy Endpoint Analysis

The analyses for the primary endpoint SVR12 will be conducted for Region 1, Region 2, and Overall after all subjects complete the posttreatment Week 12 visit or prematurely discontinue from study. All the safety and efficacy data through the posttreatment Week 12 visit will be cleaned, finalized and included for the analysis.

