3.4. Missing Data and Outliers

3.4.1. Missing Data

In general, missing data will not be imputed unless methods for handling missing data are specified.

For missing last dosing date of study drug, imputation rules are described in Section 3.7.1. The handling of missing or incomplete dates for adverse event (AE) onset is described in Section 7.2.5.2, and for prior and concomitant medications in Section 7.5.

For analyses of categorical HCV RNA data, missing posttreatment HCV RNA data will have the missing data imputed. Missing on-treatment HCV RNA will have the missing data imputed up to the time of the last dose (for on-treatment displays). If the study day associated with the last dosing date is greater than or equal to the lower bound of a visit window, and the value at the visit is missing, the value will be imputed. If the study day associated with the last dosing date is less than the lower bound of a visit window then the on-treatment value at that visit will remain missing.

If a HCV RNA data point is missing and is preceded and followed in time by values that are “< LLOQ target not detected (TND)”, then the missing data point will be set to “< LLOQ TND”. If a data point is missing and preceded and followed by values that are “< LLOQ detected”, or preceded by “< LLOQ detected” and followed by “< LLOQ TND”, or preceded by “< LLOQ TND” and followed by “< LLOQ detected”, then the missing value will be set to “< LLOQ detected”. In these situations the data point will be termed a bracketed success; otherwise, the data point will be termed a bracketed failure (ie, \geq LLOQ detected). If a data point is missing and is not bracketed, the missing data point will also be termed a failure (ie, \geq LLOQ detected) except for SVR24, which will be imputed according to SVR12 status. Success for SVR12 who have no further HCV RNA measurements collected will be counted as a success for SVR24 due to the high correlation between these 2 endpoints.

For the analyses of continuous HCV RNA efficacy data, when and only when a missing HCV RNA value is imputed as < LLOQ TND or < LLOQ detected according to the imputation rule described above, the corresponding continuous value will be imputed to LLOQ – 1 IU/mL. No other imputation will be performed for continuous HCV RNA data.

For health-related quality of life data SF-36, missing data will not be imputed.

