3.7.3. Selection of Data in the Event of Multiple Records in an Analysis Window

Depending on the statistical analysis method, single values may be required for each analysis window. For example, change from baseline by visit usually requires a single value, whereas a time-to-event analysis would not require 1 value per analysis window.

If multiple valid nonmissing numeric observations exist in an analysis window, records will be chosen based on the following rules if a single value is needed:

- For baseline, the last available record on or prior to the date of the first dose of study drug will be selected. If there are multiple records with the same time or no time recorded on the same day, average (arithmetic mean) will be used for the baseline value. If multiple ECG measurements occur on the same day prior to first dose of any study drug, the average will be used considered as baseline value for continuous data, regardless of the timing of these multiple ECG measurements.

- For postbaseline visits:
 - The record closest to the nominal day for that visit will be selected except for HCV RNA posttreatment follow-up visits, for which the latest record in the analysis window will be selected.
 - If there are 2 records that are equidistant from the nominal day, the later record will be selected.
 - If there is more than 1 record on the selected day, the average will be taken, unless otherwise specified.

If multiple valid nonmissing categorical observations exist in a window, records will be selected as follows:

- For baseline, the last available record on or prior to the date of the first dose of study drug will be selected. If there are multiple records with the same time or no time recorded on the same day, the value with the lowest severity will be selected (eg, normal will be selected over abnormal). If multiple ECG measurements occur on the same day prior to the first dose of any study drug, the value with the lowest severity will be selected regardless of the timing of these multiple ECG measurements.
- For postbaseline visits, follow the same rules described above for postbaseline numeric observations, except that if there are multiple records on the same day, the most conservative value will be selected (eg, abnormal will be selected over normal).

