6.1.2. Statistical Hypothesis for the Primary Efficacy Endpoint

In the primary efficacy analysis, the SVR12 rate in Region 1 will be compared to the pre-specified performance goal of 85% by using a two-sided exact one-sample binomial test at the 0.05 significance level. The null (H0) and alternative (H1) hypotheses used to assess superiority of SOF/VEL in Region 1 relative to the performance goal of 85% are:

- H0: SVR12 rate = 85%
- H1: SVR12 rate \neq 85%

It is difficult to characterize a single historical control rate for all genotypes included in this study given the different standards of care of each genotype (some of which include interferon), and the lack of historical data for genotype 4, 5, and 6 participants. Given these difficulties, rather than use a historical control rate as the basis for assessing the primary endpoint, a pre-specified performance goal is defined as a benchmark against which the efficacy of SOF/VEL will be tested. The benchmark sets a high bar of 85%. The basis for this benchmark includes the overall trend toward increasing SVR rates in recent years, the higher SVR rates observed with Peg-IFN + RBV treatment in Chinese and other Asian subjects {Yu 2009} compared with other races, and the general appeal of using a fixed clinically relevant threshold as a measure of treatment benefit {Weins 2013} of SOF/VEL.

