6.2.2. Analysis Methods for Secondary Efficacy Endpoints

For analyses of HCV RNA < LLOQ by visit while on treatment and during the posttreatment (SVR) follow-up period, subjects will be assigned a value at each visit based on the analysis visit windows specified in Section 3.7.2. Missing values will be imputed based on the categorical imputation rules described in Section 3.4.1. The two-sided 95% exact confidence interval based on Clopper-Pearson method will be provided for the percentage of subjects with HCV RNA < LLOQ at each visit by region and genotype. The overall category for “HCV RNA < LLOQ” will be split into the following 2 subcategories: “< LLOQ TND” for subjects with target not detected and “< LLOQ detected” for subjects with < LLOQ detected in tabular displays.

Graphs for the percentage of subjects with HCV RNA < LLOQ over time during treatment will be displayed.

Summary statistics will be presented for absolute values and change from baseline in HCV RNA (\log_{10} IU/mL) by visit through EOT. Imputation rules described in Section 3.4.1 will be used to assign HCV RNA values for missing values at a visit that are bracketed by “< LLOQ TND” and/or “< LLOQ detected”. Otherwise, a missing = excluded analysis will be performed. Plots of the mean \pm SD and median (Q1, Q3) of absolute values and changes from baseline in HCV RNA through EOT will be presented.

For the SVR12 endpoint analysis, a summary table of the number and percentage of subjects with SVR12, virologic failure (VF), and Other by region and genotype will be created. All subjects who achieve SVR12 will be categorized as SVR12. Virologic failure will be descriptively summarized as “on-treatment virologic failure” and relapse (which will be broken down by study drug completed yes/no). Subjects who do not achieve SVR12 and do not meet criteria for VF will be categorized as “Other”. The denominator for relapse will be the number of subjects who had HCV RNA < LLOQ on their last observed on-treatment HCV RNA measurement; otherwise, the denominator will be the number of subjects in the FAS.

[figure not shown]
A concordance table between SVR12 and SVR24 will be provided by region and genotype. Subjects with both observed SVR12 and observed SVR24 data will be included for this analysis.

Drug resistant substitutions will be analyzed and presented as part of the Clinical Study Report.

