7.2.6. Summaries of Adverse Events and Deaths

A brief high-level summary of TEAEs will be provided by region and by the number and percentage of subjects who had the following: any AE; any AE of Grade 3 or above; any AE of Grade 2 or above; any treatment-related AE; any treatment-related AE of Grade 3 or above; any treatment-related AE of Grade 2 or above; any SAE; any treatment-related SAE; any AE that led to premature discontinuation of SOF/VEL, any AE that led to interruption of SOF/VEL. All deaths (including those that are treatment emergent and those that are not treatment emergent) observed during the study will also be summarized and included in this table.

Adverse event summaries will provide the number and percentage of subjects with TEAEs by SOC and PT, by region based on the Safety Analysis Set as follows:

- All AEs
- AEs of Grade 3 or above
- AEs of Grade 2 or above
- All treatment-related AEs
- Treatment-related AEs of Grade 3 or above
- Treatment-related AEs of Grade 2 or above
- All SAEs
- All treatment-related SAEs
- AEs leading to premature discontinuation of SOF/VEL

- Adverse Events Leading to Interruption of SOF/VEL
- Deaths

Multiple events will be counted only once per subject in each summary. Adverse events will be summarized and listed by region first in alphabetic order of SOC and then by PT in order of descending incidence within the Overall group within each SOC. In summaries by severity grade, the most severe grade will be used for those AEs that occurred more than once in an individual subject during the study.

In addition to the above summary tables, TEAEs will be summarized by PT only and by region, in order of descending incidence in the Overall group for:

- All AEs
- AEs that occurred in at least 5% of subjects within any region
- AEs of Grade 3 or above
- All treatment-related AEs
- All SAEs
- AEs leading to premature discontinuation of SOF/VEL
- AEs leading to interruption of SOF/VEL

In addition to the summaries described above, data listings by region and subject ID (in ascending order) will be provided for the following:

- All AEs
- AEs of Grade 3 or above
- SAEs
- Deaths
- AEs leading to premature discontinuation of SOF/VEL
- Adverse Events Leading to Interruption of SOF/VEL
- AE with changes other than resolution dates between the SVR12 and SVR24 analyses (provided only at the final analysis)

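### Does the SAP leave open which HCV RNA values after the Week 12 visit count towards SVR12, and whether SVR12 is derived again at the final analysis?

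*SAP*

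**What the plan says.** - **Timing and data (SAP 2.2.2).** The primary analysis is run "after all subjects complete the posttreatment Week 12 visit or prematurely discontinue from study". Its data are defined by visit: "All the safety and efficacy data through the posttreatment Week 12 visit will be cleaned, finalized and included for the analysis". Section 2.3 places the final analysis after study completion and does not mention SVR12.
- **Window (SAP 3.7.2, Table 3-2).** For HCV RNA, FU-12 covers follow-up Days 70 to 146 and FU-24 covers Days 147 to 210. Footnote a equates each FU-x visit with the posttreatment Week-x follow-up visit.
- **Choice of record (SAP 3.7.3).** Posttreatment HCV RNA visits are the exception to the closest-record rule, "for which the latest record in the analysis window will be selected".
- **Missing values (SAP 3.4.1).** A gap with HCV RNA below LLOQ on both sides is a success: "In these situations the data point will be termed a bracketed success; otherwise, the data point will be termed a bracketed failure". An unbracketed gap is a failure, "except for SVR24, which will be imputed according to SVR12 status".
- **The test (SAP 6.1.2).** "In the primary efficacy analysis, the SVR12 rate in Region 1 will be compared to the pre-specified performance goal of 85" percent.
- **Later use of SVR12.** Section 6.2.2 plans this display: "A concordance table between SVR12 and SVR24 will be provided by region and genotype". It is limited to subjects with both results observed. Section 7.2.6 plans a listing of "AE with changes other than resolution dates between the SVR12 and SVR24 analyses (provided only at the final analysis"); SVR12 status has no counterpart.

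**The concern.** The Week 12 visit is scheduled at Day 84 ± 5 (Appendix 1), that is Days 79 to 89, but the FU-12 window stays open to Day 146. The bracketing rule in Section 3.4.1 carries no data cut. Some subjects will have Week 24 results when the last subject reaches Week 12. If programmers used whatever was in the database, early enrollees could have a missing FU-12 value rescued by a Week 24 result and late enrollees could not.

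The case is foreseeable. Under Appendix 1, footnote i, a subject below LLOQ at posttreatment Week 4 who misses Week 12 can still attend Week 24. Section 2.3 does not say whether SVR12 is then locked or derived again. Two analysts might report different SVR12 counts, and the final report might show a rate that differs from the tested one. Near the decision boundary, one subject decides the test.

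**Working it through.** **1. The plan's own figure.** Inputs from SAP 1.3: n = 260 in Region 1, performance goal 85%, alternative 85% + 6 points = 91%, two-sided exact binomial test at 0.05.
- The smallest count r with P(X ≥ r | 260, 0.85) ≤ 0.025 is r = 233, with upper tail 0.0193.
- Power is P(X ≥ 233 | 260, 0.91) = 81.5%. The stated power of more than 80% reproduces.

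**2. The boundary** (p is twice the smaller tail; Clopper-Pearson interval).

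| Successes | Rate | p | 95% CI |
|---|---|---|---|
| 232/260 | 89.2% | 0.060 | 84.8% to 92.7% |
| 233/260 | 89.6% | 0.039 | 85.3% to 93.0% |

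**3. Chance that a status change would cross the boundary.** The SAP gives no rate of such changes, so these figures are conditional on a change occurring. The 91% rate is the SAP's alternative; 93% and 95% are assumed to show the range.

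| Change | Crosses if the count was | 91% | 93% | 95% |
|---|---|---|---|---|
| 1 failure to success | 232 | 5.0% | 0.7% | 0.01% |
| 3 failures to success | 230 to 232 | 11.9% | 1.3% | 0.01% |
| 1 success to failure | 233 | 6.0% | 1.1% | 0.02% |

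These matter only if the SAP leaves the status used in the test open. Steps 4 and 5 address that.

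**4. A missing FU-12 value at the primary analysis.**
- Any value on Days 70 to 146 is itself FU-12. A later bracket must therefore come from Day 147 or after, which is FU-24 or later.
- The Section 2.2.2 cut is defined by visit, not by calendar date. FU-24 values fall outside it for every subject, whenever enrolled.
- The gap is then unbracketed, and Section 3.4.1 scores it as failure. This is the conservative direction for a test against a fixed goal.

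**5. An unscheduled sample after the Week 12 clinic date.**
- By Table 3-2 footnote a, the posttreatment Week 12 visit in the analysis is FU-12, which runs to Day 146. The ± 5 days in Appendix 1 is a scheduling tolerance.
- A sample on Day 120, say, is FU-12 data, and as the latest record in the window it is the one used.
- Appendix 1 schedules no HCV RNA between Weeks 12 and 24, so only unscheduled samples are involved.

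**6. Use of SVR12 at the final analysis.**
- *Concordance table:* it needs observed SVR12 and observed SVR24. A subject with a missing, bracketed FU-12 is not in it.
- *SVR24 imputation:* carrying SVR12 forward concerns subjects with no further HCV RNA. A subject whose FU-12 gap is bracketed by an FU-24 value has SVR24 observed.
- *Test:* Section 6.1.2 ties it to the primary efficacy analysis, and no second test is planned.

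**7. What could still move.** A descriptive SVR12 rate at the final analysis, by 1/260 = 0.38 points per Region 1 subject re-scored. If 1%, 2%, 3% or 5% of the 260 (assumed) had a missing FU-12 value and later values below LLOQ, that is 3, 5, 8 or 13 subjects, or 1.2, 1.9, 3.1 or 5.0 points, all upward.

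**The case for a change.** The strongest argument for acting is that Section 2.2.2 states what is included and never says that later values already in hand are ignored. It does not cite Table 3-2, so the reading in steps 4 and 5 joins separate sections. Even on that reading, a missing FU-12 value is a failure at the primary analysis and a bracketed success if Section 3.4.1 is rerun on final data. The primary endpoint could then appear with two rates, and subjects could move from the Other category to SVR12 in the Section 6.2.2 outcome table. For the last subjects enrolled, the FU-12 window may also still be open at the cut, so an unscheduled sample could arrive later. Two or three sentences and a short listing would close all this at little cost.

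Part of this stands: the SAP does not say whether SVR12 is locked or re-derived. The rest is weaker. A cut stated by visit excludes later visits on its ordinary reading. The open window matters only for an unscheduled sample taken after the cut and by Day 146. The crossing probabilities in step 3 would describe harm only if the test were repeated, and it is not. A remedy can also do damage: limiting the derivation to values up to each subject's Week 12 clinic date would contradict the Day 146 limit and the latest-record rule. A subject below LLOQ on Day 84 and at or above LLOQ on Day 120 would then count as a success, which is less conservative than the present plan.

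**Conclusion.** No change follows. Followed as written, the SAP gives one sound and conservative SVR12 status for the Region 1 test: HCV RNA through the FU-12 window, latest record, missing scored as failure, the same for all enrollees. Type I error, the 233/260 threshold and the 81.5% power are unaffected. What is left is an unwritten convention about re-scoring a missing FU-12 value at the final analysis. It touches descriptive displays only, at 0.38 points per Region 1 subject, for a number of subjects the SAP does not give and that is probably small. Analysts would ordinarily keep the tested SVR12 result as the primary one and footnote any later difference.

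This rests on two readings: that the posttreatment Week 12 visit in Section 2.2.2 is the FU-12 visit of Table 3-2, and that the test is performed once, at the primary analysis. The text supports both.
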